A technology-based approach using computers and mobile devices (smart phones and tablets) promises to meet this necessity with high flexibility and accessibility, and minimizes the cost of the intervention in busy health care settings. Also, a technology-based intervention that does not involve face-to-face interactions could work better for many women from cultures where breast cancer is still a stigmatizing experience. Bespite the high potential, few technology-based interventions are available for ethnic minority breast cancer survivors, especially for Asian Americans. Therefore, based on Preliminary Studies (PSs), the research team has developed and pilot-tested a theory-driven technology-based information and coaching/support program that: (a) is tailored to Asian American breast cancer survivors by incorporating actual data on individual sub-ethnic groups cultural attitudes from PSs; (b) uses multiple languages; (c) provides both group and individual (real-time and personalized) coaching/support by culturally matched bilingual health care providers; (d) incorporates peer support through a social media function; and (e) integrates existing general and culture-specific evidence-based educational content from scientific authorities. Among over 71 sub-ethnic

groups of Asian Americans,⁴⁶ only three sub-ethnic groups (Chinese, Korean, and Japanese) were selected for the program development for the convenience of the approach (e.g., language). Within Asian Americans, Chinese are the largest sub-ethnic group,^{47,48} Koreans are the fastest growing sub-ethnic group,^{47,48} and Japanese are the sub-ethnic group at the highest risk of breast cancer.^{1,2,11,49}

Goals/Aims

The purpose of the proposed randomized intervention study is to test the efficacy of the technology-based information and coaching/support program for Asian American breast cancer survivors (TICAA) in enhancing the women's breast cancer survivorship experience.

The **specific aims** of the study are to:

Aim 1. Determine whether the intervention group (who uses the TICAA and the information on breast cancer by the American Cancer Society [ACS]) will show significantly greater improvements than the control group (who uses only the information on breast cancer by the ACS) in **primary outcomes** of the TICAA (needs for help, physical and psychological symptoms, and quality of life) from baseline (pre-test) to Time Points 1 (post 1-month; primary) and 2 (post 3-months; secondary).

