Aim 2. Identify theory-based variables (attitudes, self-efficacy, perceived barriers, and social influences related to breast cancer survivorship) that **mediate** the intervention effects of the TICAA on the primary outcomes of the TICAA from baseline to Time Point 1.

Aim 3 (exploratory). Explore whether the effects of the TICAA on the primary outcomes are **moderated** by background factors and disease factors.

Study Design

Organizational structure of the study team:

This is a PI initiated R01 research project that is funded by the National Cancer Institute (National Institute of Health). Due to PI's move from Duke University to Emory University, the study is being transferred from Duke Univ. to Emory University. This is the fourth year of the total 5 year of funding. This IRB approval is needed for the grant transfer.

The study team includes the PI, 1 Co-Investigator, 1 Statistician, multiple Consultants, 3 interventionists and 1 or 2 research assistants. Except the consultants, all research team members will be Emory affiliated. The research team will conduct the study at School of Nursing, Emory University.

Setting and location:

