A total of 330 Asian American breast cancer survivors will be recruited. Because information is limited on which to base power analyses, estimates are based on a two-sided Mann-Whitney test (assuming a uniform distribution) using an estimated effect size equal to 1/2 of a standard deviation, as suggested in the literature. In addition to being clinically meaningful, large effect sizes demonstrated in PS4 suggest that 0.5*SD is a statistically meaningful effect size to assume. Sample size is based on 80% power, and a type I error rate equal to 0.00625 to account for eight primary outcome measures modeled within the two primary aims (group main effects). Accordingly, group sample sizes of 105 each achieve 80% power to detect a difference of 0.5*SD between group means overall in a single follow-up period. The primary analysis will be an assessment of differences by intervention group in changes from baseline to Time Point 1, or one month post intervention. A secondary analysis will include similar modeling for sustainability of

intervention effects, or for changes from baseline to Time Point 2. Assuming an attrition rate of 35% by the Time Point 2, 330 Asian American breast cancer survivors would be an adequate number for the study with multiple outcomes. Considering the attrition rates reported in the literature^{66–68} and in PSs, the assumption of a 35% attrition rate is reasonable.

At the completion of their participation, the participants will be reimbursed with \$50 electronic gift cards for their participation. The reimbursement will be prorated. The participants will be allowed to choose "do not want to respond", which will NOT be considered missing data. The amount was determined based on preliminary studies.

o Description of recruitment materials and their use

Sample study announcement, sample study announcement in flyer format, and flyer for TICAA recruitment will be distributed through and displayed on cancer support groups and communities/groups for Asian Americans.

o Describe the procedures for data collection

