The data are mainly collected through the Internet survey questionnaire. When potential participants visit the project Web site (after receiving/reviewing a study announcement), they will be asked to review the informed consent. When participants click I agree to participate, they will have given their consent. Then, after checking them against the inclusion criteria and quota requirements, only those who meet the criteria and requirements will be automatically assigned a serial number, and randomized into two groups using an automated random number generator accessible through the Web site.

Then, the women will be asked to fill out the Internet survey questionnaire (if requested, paper-and-pencil questionnaires will be provided/used, or research staff will assist in administering the Internet surveys over the phone.) and sign up the Web site by creating their own ID and passwords. Whenever they visit the Web site, they need to use the ID and passwords to log in the site. If they want, they can change their ID and passwords. Then, both groups will be provided with an electronic instruction sheet on when they need to come back and fill out additional questionnaires and/or use the program.

Biweekly, the research team will send reminders and thank-you emails. Two weeks before the end of the 1st month, both groups will be asked to fill out the next set of the instruments by the end of the 1st month. Then, 2 weeks before the end of the 3rd month, both groups will be asked to fill out the next set of the instruments by the end of the 3rd month.

O Description of research instruments to be used (e.g., questionnaires, surveys, interview or focus group guides, scales)

Multiple instruments will be used: the Support Care Needs Survey-34 Short Form (SCNS-34SF),⁵⁰ the Memorial Symptom Assessment Scale-Short Form (MSAS-SF),⁵¹ the Functional Assessment of Cancer Therapy Scale-Breast Cancer (FACT-B),⁵² the modified Questions on Attitudes, Self-Efficacy, Perceived Barriers, and Social Influences (QASPS),⁵³ the Cancer Behavior Inventory (CBI),^{54,55,56} the Perceived Isolation Scale (PIS),^{57,58} the Personal Resource Questionnaire (PRQ-2000),⁵⁹ and 27 questions on background characteristics, level of acculturation, and disease factors. The reliability and validity of all the instruments have been established among Asian Americans. Cronbach's alpha of individual instrument ranged from .76 to .96 among Asian Americans.

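### The sample size divides alpha over eight primary outcome measures that are never listed, and the analysis section states no alpha or multiplicity method; list the family and test it with Holm

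*Combined protocol and SAP*

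**What the plan says.** The sample-size paragraph (under Recruitment) sets "a type I error rate equal to 0.00625 to account for eight primary outcome measures modeled within the two primary aims (group main effects"). It states that "estimates are based on a two-sided Mann-Whitney test (assuming a uniform distribution"), "using an estimated effect size equal to 1/2 of a standard deviation", and concludes that "group sample sizes of 105 each achieve 80% power to detect a difference of 0.5*SD between group means overall in a single follow-up period". It then says: "Assuming an attrition rate of 35% by the Time Point 2, 330 Asian American breast cancer survivors would be an adequate number". The same paragraph makes the change from baseline to Time Point 1 primary and the change to Time Point 2 secondary.

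Goals/Aims, Aim 1, gives the primary outcomes as "needs for help, physical and psychological symptoms, and quality of life". Aim 2 names four theory-based variables (attitudes, self-efficacy, perceived barriers, social influences) as possible mediators of "the intervention effects of the TICAA on the primary outcomes of the TICAA from baseline to Time Point 1". It does not call them primary outcomes. Only Aim 3 is labelled exploratory.

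The description of research instruments lists SCNS-34SF, MSAS-SF, FACT-B, "the modified Questions on Attitudes, Self-Efficacy, Perceived Barriers, and Social Influences (QASPS"), CBI, PIS and PRQ-2000. It does not assign an instrument to an outcome or a mediator, and it does not say which scores are primary.

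Under the plans for analysis, the Aim #1 paragraph fits separate models for each outcome measure, but does not list the measures. None of the analysis paragraphs (preliminary analysis, Aim #1, Aim #2, Aim #3) states a significance level or a multiplicity procedure.

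**The concern.** The number that fixes the test level is eight, while the aims attach the word primary to three or four outcomes. A reader cannot tell which eight scores are meant. The level 0.00625 appears only where the trial is sized and is not carried into the analysis.

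Two analysts could therefore follow the document faithfully and test Aim 1 differently. One would use 0.00625 for each outcome, taking it from the sample-size text. The other would use the customary 0.05, because the analysis text sets nothing else. An outcome with a p-value of 0.02 would be an efficacy finding for the second and not for the first. Because no scores are named, the choice between totals and subscales is also open. The efficacy conclusion could then depend on choices made after the data are seen.

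**Working it through.** **1. The plan's own figures.** The 0.05 family-wise level is inferred, not stated: 0.05/8 = 0.00625 exactly.

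Sample size per group, two-sided, 0.5 SD, 80% power:
- Normal approximation: n = 2(z₁₋α/₂ + z₀.₈)²/d² = 2(2.734 + 0.842)²/0.25 = 102.3, so 103.
- Noncentral t: 104.2, so 105. The large-sample efficiency of Mann-Whitney for a uniform distribution is 1.0, so 105 is unchanged.
- Power at 105 per group: 81.3% (normal) or 80.4% (t).
- Attrition: 210/(1 − 0.35) = 323.1, so 324. The planned 330 covers this (330 × 0.65 = 214.5, about 107 per group).

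The figures reproduce by the usual efficiency-factor method. As a side check, direct simulation of Mann-Whitney on uniform data shifted by 0.5 SD gave about 75% power at 105 per group. That is a separate matter and does not bear on this point.

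**2. What the eight could be.**

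| Count | Fit with the text |
|---|---|
| 4 Aim 1 outcomes + 4 Aim 2 mediators | Best fit: Aims 1 and 2 are the non-exploratory aims, and the Aim #2 paragraph plans a comparison of the groups on the mediators |
| 4 outcomes × 2 time points | Poor fit: Time Point 2 is secondary |
| 4 outcomes counted under each of two aims, or subscores | Not excluded, but stated nowhere |

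**3. If Aim 1 is tested at a flat 0.00625.** The Bonferroni bound on error within Aim 1 is 4 × 0.00625 = 0.025, or 3 × 0.00625 = 0.01875. Both are below 0.05, so this route is conservative for Aim 1.

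**4. If each Aim 1 outcome is tested at 0.05.** The chance of at least one false positive when no effect is real:

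| Outcomes | Independent, 1 − 0.95ᵏ | Correlation 0.5 (assumed) | Correlation 0.7 (assumed) |
|---|---|---|---|
| 3 | 14.3% | 12.5% | 11% |
| 4 | 18.5% | 16% | 13% |

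**5. Holm over the same eight.** Holm compares the smallest p-value with 0.05/8, the next with 0.05/7, and so on, stopping at the first failure. It rejects everything that a flat 0.00625 rejects. Simulation with normal test statistics, 105 per group, true effects of 0.5 SD, correlation 0.5 to 0:

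| Real effects among the eight | Power per outcome, flat 0.00625 | Power per outcome, Holm |
|---|---|---|
| 4 | 81% | 84–85% |
| 8 | 81% | 90–93% |

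Family-wise error under Holm stayed at or below 5%.

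**6. For scale, a family of Aim 1 outcomes only.** At 105 per group, t-test power at the Bonferroni level is 86.4% for four outcomes (0.0125) and 88.6% for three (0.0167), against 80.4% at 0.00625.

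**The case against.** The strongest defence is that the plan is coherent as it stands. The sample-size paragraph says openly that its count spans two aims and concerns group main effects. The Aim #2 paragraph does ask whether the intervention group improves more on the mediators. Four outcomes and four mediators then make eight group comparisons, and 0.05/8 is a valid Bonferroni split. The trial was sized to pay for it, and the result is conservative for Aim 1. All of this stands.

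Several stronger readings are tempting, and the documents do not support them:
- A reader might infer that eight can be reached only by adding the mediators. That is the most natural count, but the text does not exclude others.
- A reader might infer that Aim 1 is bound to 0.00625. The level appears only in the sizing text, and no analysis paragraph applies it.
- A reader might infer that half of the error allowance is wasted, since four outcomes at 0.00625 use only 0.025. On the four-plus-four count, the mediator comparisons use the other half.
- A reader might infer a miscount because mediation involves 4 × 3 to 4 × 4, or 12 to 16, chains. The count is limited to group main effects, so the chains fall outside it.

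It is also fair to say that 105 per group reflects attrition by Time Point 2, while the primary test is at Time Point 1, where attrition is not stated. If 20% were lost by then (an assumption), 132 per group would remain, and power would be 90% at 0.00625 against 94% at 0.0125. With no loss (165 per group) it would be 96% against 98%. The power given up may therefore be smaller than the 105-per-group figures suggest.

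The missing list and the missing analysis rule are not answered by any of this.

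**Conclusion.** The point holds as a gap in definition and in the analysis rule. The arithmetic is sound. The eight measures are not listed, Aim 1 names three or four primary outcomes, and the analysis section sets no alpha and no multiplicity method. The mismatch in count does not by itself inflate type I error, and it gives no reason to change the sample size.

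The cost depends on which route analysts take, and the plan allows either. A flat 0.00625 loses about 3 to 4 points of power per outcome against Holm over the same eight if four effects are real, and 9 to 12 points if all eight are. Testing at 0.05 each leaves a family-wise error of about 12% to 19% over three or four outcomes. These figures assume 0.5 SD effects, 105 per group, normal test statistics and correlations between 0 and 0.5. More participants at Time Point 1 would shrink the power differences.

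Holm removes both problems under either reading of the family. Whether the mediators belong in the family is a trade-off for the sponsor, and the documents do not make their inclusion an error.

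**What to change.** In the Aim #1 paragraph of the analysis plan:
- List every member of the family behind the eight, giving the construct, instrument and score for each, and say that the test is the group comparison at Time Point 1.
- State that the family is tested with Holm at two-sided family-wise 0.05, in place of a flat 0.00625 or an unstated level.
- Report other scores, subscales and Time Point 2 as secondary.

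In the sample-size paragraph, keep 330 and describe 0.00625 as the conservative level used for sizing. If the sponsor takes the mediators out of the family, the reference there to eight primary outcome measures must be corrected to match.

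The cost is wording: no further data and no change in sample size. Group differences on mediators would lose primary status only if the sponsor removes them. Timing matters, because the population section says that 210 of the 330 participants have already completed, and the documents do not say whether outcomes have been looked at. The change should be dated and made before outcomes are examined by arm. If they have been examined, it needs a documented justification, above all if the family is made smaller, because that relaxes the first Holm step (for example from 0.00625 to 0.0125 with four members). Listing the planned eight does not loosen anything.

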O Describe any other study-related interactions or interventions: **The Intervention: The**TICAA

This study consists of two groups of research participants: (a) 165 Asian American breast cancer survivors (55 per sub-ethnic group) who do not use the TICAA, but use the information on breast cancer by the American Cancer Society (ACS)(a control group); (b) 165 Asian American breast cancer survivors (55 per sub-ethnic group) who use the TICAA and the information by the ACS (an intervention group). The ACS website includes information on treatment, prevention, genetics, causes, screening, testing, coping, clinical trials, research findings, and statistics related to breast cancer in multiple languages including Mandarin Chinese and Korean. At the completion of the study, both will be allowed to use or continue to use the TICAA.

Theoretical Bases, Information Architecture, and Menus. The TICAA was developed based on the findings from PSs using the information mapping approach.⁶⁹ The TICAA is theoretically based on the Bandura's theory. Based on the Bandura's theory, ^{70–72} most self-management programs include coaching/support and information interventions as part of the program content.⁷³ Likewise, the TICAA includes group and individual (real-time and personalized) coaching/support by health care providers, peer coaching/support, and information to change the women's attitudes, self-efficacy, perceived barriers, and social influences. The TICAA uses a free-form matrix information architecture⁷⁴ and includes menus based on the three components (see below). Graphic User Interface controls⁷⁵ (e.g., push buttons, check boxes, drop-down lists) are used. Presentation styles (e.g., colors, menus, etc.) are tailored based on PSs.

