Aim #1: Effects on Primary Outcomes. Separate intent-to-treat general linear models 86 will be used to examine differences in continuous outcome measures by intervention group at each time point, adjusting for baseline outcome and any variables that demonstrate imbalances in preliminary analyses. Model assumptions will be assessed, and modifications will be implemented as necessary to improve mode fit. Differences in continuous outcome measures over time will be examined using an intent-to-treat linear mixed-model growth curve analysis with SAS Proc Mixed.86 Mixed models will be used in which all available data collected during follow-up is used.87,88 Separate mixed effects regression models will be generated for each outcome measure. Both random slopes and intercepts will be modeled to represent the subject level deviation from the average, or fixed-effect, slope over time and intercept, respectively. Restricted maximum likelihood estimation will be used, and the most appropriate covariance structure will be examined. The outcomes will be analyzed as repeated observations of the dependent variables, with mean-centered baseline outcome scores serving as a covariate. Other predictors will include intervention group, time from baseline to follow-up, the interaction of group and time, and the interaction of baseline measures and time. Baseline outcome and group will be analyzed as time-independent covariates. Other demographic or treatment timeindependent variables identified in preliminary analyses may be included as covariates. Main effects and higher order interaction terms will be examined. The Akaike information criterion will evaluate overall model fit and to select the best-fitting longitudinal change pattern.89

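### Minor: for the Mann-Whitney test on uniform data named in the sample-size paragraph, 105 per group gives about 75% power under a location shift, not 80%

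*Combined protocol and SAP*

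**What the plan says.** The sample-size paragraph under Recruitment opens with a caveat, "Because information is limited on which to base power analyses", and then states its basis: "estimates are based on a two-sided Mann-Whitney test (assuming a uniform distribution", with an effect of half a standard deviation. It uses "a type I error rate equal to 0.00625 to account for eight primary outcome measures modeled within the two primary aims (group main effects", and concludes that "group sample sizes of 105 each achieve 80% power to detect a difference of 0.5*SD between group means overall in a single follow-up period". It then allows for dropout ("Assuming an attrition rate of 35% by the Time Point 2") and calls a total of 330 adequate. The intervention section gives the allocation, with a control arm of "165 Asian American breast cancer survivors (55 per sub-ethnic group) who do not use the TICAA" and an intervention arm of the same size.

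The analysis section (Aim #1: Effects on Primary Outcomes) does not use a Mann-Whitney test. It compares the groups at each time point with general linear models, "adjusting for baseline outcome and any variables that demonstrate imbalances in preliminary analyses", and adds mixed models over time.

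**The concern.** The paragraph names the test, distribution, effect size, alpha and group size, so its power can be checked. The figure of 105 is exactly what a two-sample t-test needs. A rank test on uniform data, with a shift as large as half an SD and so strict an alpha, should need more. This is the plan's only power statement and the only numerical support for 330. If it does not follow from its own stated method, a reader cannot tell what power the trial has, for that test or for the model that will be fitted.

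**Working it through.** **Inputs.** From the Recruitment section: two-sided test, alpha = 0.05/8 = 0.00625 (normal critical value 2.734), difference 0.5 SD, uniform data, 105 per group, 35% attrition by Time Point 2. From the intervention section: 165 per group.

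**1. Where 105 comes from.** Two-sample t-test, noncentral t with 2n − 2 degrees of freedom and noncentrality 0.5·√(n/2). Power is 79.9% at n = 104 and 80.4% at n = 105, so 105 is the smallest n that reaches 80%.

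The usual shortcut for Mann-Whitney divides the t-test n by the asymptotic relative efficiency, 12·σ²·(∫f²)². For a uniform on (0,1), σ² = 1/12 and ∫f² = 1, so the efficiency is 1 and n stays at 105. This reproduces the stated figure. That the authors took this route is inferred; the plan gives no formula or software.

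**2. Direct calculation for the named test.** A uniform distribution is fixed by its mean and SD. Two uniform groups with one SD and means 0.5 SD apart therefore differ by a pure shift.

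- Shift as a fraction of the range: θ = 0.5/√12 = 0.1443.
- P(Y>X) = 1 − ½(1 − θ)² = 0.634. The small-shift approximation gives 0.5 + θ = 0.644, which is too high for a shift of this size.
- Mean of U above its null value at n = 105: 105² × 0.1339 = 1476.5.
- Null SD of U: √(n²(2n+1)/12) = 440.3.
- SD of U under the alternative: √(n²[p(1−p) + 2(n−1)(p₂ − p²)]), with p = 0.6339 and p₂ = θ + (1 − θ³)/3 = 0.4767, gives 417.3.
- Power ≈ Φ((1476.5 − 2.734 × 440.3)/417.3) = Φ(0.653) = 74.3%.

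Simulation (300,000 trials, continuity correction) agrees. With no shift it rejects at 0.0062, as it should.

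| n per group | Analytic | Simulated |
|---|---|---|
| 105 | 74.3% | 74.6% |
| 107 (165 × 0.65 = 107.3) | 75.4% | 75.6% |
| 116 | 79.8% | 79.7% |
| 117 | 80.3% | 80.3% |

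A t-test simulated on the same uniform data at n = 105 has 80.5%. The gap therefore belongs to the rank test and is not caused by uniform data as such.

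**3. Sensitivity to the alternative** (Mann-Whitney, 105 per group, simulated).

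- Normal data, shift: 77.7%.
- Logistic data, shift: 84.2%.
- One group uniform, the other kept within the same range with a mean 0.5 SD higher: about 82% (81.9% to 82.5% over four shapes). Here P(Y>X) is exactly 0.644.

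**4. The planned baseline-adjusted model** (105 per group, alpha 0.00625, 2n − 3 degrees of freedom, r = assumed correlation of baseline with follow-up). The plan does not say which SD the 0.5 refers to. The standardised effect is 0.5/√(1 − r²) if it is the SD of the outcome score, or 0.5·√(2/(1 + r)) if it is the SD of the change score, taking equal SDs at both times.

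| r | Outcome-score SD | Change-score SD |
|---|---|---|
| 0.3 | 84.8% | 95.7% |
| 0.5 | 92.1% | 92.1% |
| 0.7 | 98.9% | 87.7% |

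For r between 0 and 1 neither effect falls below 0.5, so power does not fall below the 80.4% that applies at 0.5.

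**The case against.** The plan does not state the alternative. The outcomes are questionnaire scores, and a rigid shift moves the top of one group beyond the other's range. If scores stay within one range, power is about 82% and the stated 80% is met. The efficiency of 1 for uniform data is also a standard planning approximation, so 80% is not a slip of arithmetic. And the Mann-Whitney test is only a stand-in, adopted because planning information was limited.

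Much of this stands. The 75% rests on the shift reading, and the write-up has to say so. The within-range alternatives, however, need the second group either not to be uniform or to have a different SD, and the paragraph mentions neither. The approximation explains the 80% without making it right for a 0.5 SD shift. The stand-in argument limits the consequence, but leaves the mismatch between stated method and stated figure.

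A reader might go further and infer that the trial is underpowered, or that it should have enrolled 117/0.65 = 180 per group, 360 in total. The documents do not support that. The primary comparison uses the baseline-adjusted linear model, which exceeds 80% at 105 per group. The 35% attrition also applies by Time Point 2, which is the secondary time point.

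**Conclusion.** The point holds as a minor one. For the named test and distribution, under a location shift with a common SD, power is about 75% at 105 per group and about 76% at 107, roughly 5 and 4 points below the stated 80%. About 117 per group would be needed. The direction depends on the alternative: normal data also fall short (about 78%), while logistic data (84%) and within-range alternatives (about 82%) do not.

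The planned analysis is adequately powered at the assumed effect: 80.4% with no gain from baseline, and 85% to 99% or 88% to 96% over the assumed correlations, depending on the SD meant. What needs correcting is the power statement. The design and the enrolment of 330 are not called into question.

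**What to change.** Make one of two changes to the sample-size paragraph.

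- Keep the Mann-Whitney basis, restate its power as about 75% at 105 per group (about 117 for 80%), and say that both groups are taken as uniform with a common SD and differ by a shift.
- Or replace it with the power of the planned baseline-adjusted model at alpha 0.00625 and 105 per group: 80.4% with no baseline correlation, then about 85%, 92% and 99% for assumed correlations of 0.3, 0.5 and 0.7 if 0.5 SD refers to the outcome score, or 96%, 92% and 88% if it refers to the change score. State which SD is meant.

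The second option describes the analysis that will be done. Either costs one paragraph, with no change in enrolment, test or threshold. The drawback is a less favourable figure under the first option, and baseline correlations that must be assumed under the second.
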